## Waiver of Consent/Authorization

Indicate if you are requesting any of the following consent waivers

Waiver of consent for use of records that include protected health information (a HIPAA waiver of Authorization)

No

Waiver or alteration of consent

Yes

Waiver of documentation of consent

No

Waiver of parental consent

No

## Consent Procedures

Is eligibility screening for this study conducted under a different IRB protocol?

No

Describe procedures used to obtain consent during the screening process

At the first contact, a standardized telephone interview will be conducted, and patients who preliminarily meet entry criteria will be scheduled for a first screening visit, during which the patient will give informed consent to provide a urine sample for toxicology and urinalysis, and to undergo a Mini International Neuropsychiatric Interview (MINI), with a psychiatrist for a medical and psychiatric evaluation, as well as completion of the Hamilton Depression Scale (HAM-D) and Dissociative Experiences Scale (DES), and if still eligible, with a research assistant for serum collection (CBC, thyroid panel, Chem 20 panel including liver function tests, serum cortisol) and other diagnostic tests (EKG). We are requesting a waiver of documentation of consent (45 CFR 46.117 (c) (1)) for the phone screen only, given that a consent form for a phone screen would be the only record linking the subject and the research.

Describe Study Consent Procedures

Eligible participants will undergo an interview with one of the consenting physicians, during which information about the study will be provided. Participants will then be asked to read the consent form on their own, after which they complete a quiz and have an opportunity to ask questions. Participants will be considered eligible if they are medically healthy, cannabis dependent individuals who meet minimum use criteria, who are between the ages of 21 and 60, and who do not have a history of abuse of or adverse reaction to ketamine or benzodiazepines. Individuals with physiological dependence on certain other substances, with a history of psychotic or dissociative symptoms, with a first-degree family history of psychosis, with obesity (BMI > 32), or with cardiovascular or pulmonary disease will be excluded. Please consult the full table of inclusion/exclusion criteria in the Human Subjects section for more details.

Indicate which of the following are employed as a part of screening or main study consent procedures

Consent Form

## Justification for Waiver or Alteration of Consent

Waiver of consent is requested for the following

A waiver of consent has been requested because the first interaction with prospective participants takes place over the phone.

Explain why your research can not be practicably carried out without the waiver or alteration

Initial screenings are conducted over the phone, and therefore in-person consent at that point is impossible. If a participant is deemed likely to be eligible, he/she is invited into the office for an in-person screening, at the start of which formal, in-person consent is obtained.

Describe whether and how subjects will be provided with additional pertinent information after participation  
Subjects are provided with additional pertinent information after participation by the physician.

## Study Procedures

Describe the procedures required for this study

Design: 15 patients meeting study criteria and providing informed consent will be entered into the 6-week trial, provided behavioral treatment, and given ketamine.

At each visit, patients will provide a urine sample that will be tested semi-quantitatively for cannabis and other drugs; complete various questionnaires; and undergo a brief evaluation during which vital signs, other safety parameters, and side effects are assessed. Two visits a week will be devoted to receiving behavioral treatment, lasting approximately 50 minutes. The other regular visit will be with a psychiatrist who will review progress, document self-reported substance use, and review side effects or other adverse events to treatment; additionally, the psychiatrist is responsible for the medical care of the patient and for decisions pertaining to study discontinuation.

There are two phases:

### Phase 1 (Week 1-2)

During the first two weeks, patients will receive outpatient motivational enhancement therapy (MET) and meet with a psychiatrist twice a week. The psychotherapy sessions be taped for supervision and research purposes.

On Week 2, Day 2, patients will be asked to initiate abstinence 24 hours prior to the medication administration. On the day of abstinence initiation, they will receive an intravenous dose of ketamine (see "Infusion Procedures"). Before the scheduled outpatient infusion, an MET session will revisit goals and address ambivalence.

### Phase 2 (Week 3-6)

During the last 4 weeks, patients will begin a standardized course of mindfulness based relapse prevention (MBRP); this training will occur twice a week, and take approximately one hour a session. Alongside MBRP training, patients will meet with a psychiatrist, who will continue monitoring their drug use and side effects.

In week 3 or 4, the patients will receive a second intravenous dose of ketamine (see “Infusion Procedures”) if they have been unable to attain abstinence. Before the scheduled infusion, an MET session will revisit goals and address ambivalence.

**Infusion Procedures:** One or two ketamine infusions will take place at the BSU within the Division on Substance Abuse. Further, studies with depression have suggested that a single dose has (antidepressant) efficacy. Thus, for the purposes of this study, a single infusion may suffice to affect the outcome measures. If it does not suffice, patients will undergo a second infusion. Patients will be abstinent from intoxicants and will have not eaten since midnight prior to the infusion so as to reduce the risk of nausea, adverse interactions, and aspiration. Participants will be informed throughout the study that they may receive any of a number of substances at the infusion, including buspirone, d-cycloserine, ketamine, midazolam, memantine, saline, or any combination of these. This will serve to further disguise the administration of ketamine, and thereby further minimize the risk that patients will subsequently seek out ketamine. Ketamine hydrochloride (0.11 mg/kg 2-min bolus followed by 0.6 mg/kg over 50 minutes **for the first infusion** and 1.3 mg/kg over 90 minutes **for the second infusion**), will be prepared and packaged for slow-drip infusion by the pharmacy at NYSPI, and will be administered at 12 pm by a physician. The dose of ketamine was selected on the basis of published reports suggesting that it was sub-anesthetic and well-tolerated; it is also comparable to the dose used in the depression studies. Infusions will take place in the presence of an ACLS and BLS certified psychiatrist ([name]) who will remain available for up to two hours after the infusion is terminated and who will provide a brief safety and psychiatric evaluation at the end of the monitoring period. Blood pressure and heart rate will be monitored every five minutes beginning five minutes before the infusion and continuing after the infusion until vital signs normalize; SBP elevation > 60 mm and DBP > 40, or absolute SBP>200 and DBP>115 and HR > (220 – age) X 0.85, will result in infusion discontinuation (please see “Risks” for more information about managing BP or HR). The physician will also be responsible for decisions pertaining to the discontinuation of the infusion in the case of an adverse event. The physician will also be guiding mindfulness-based exercises for the duration of the infusion. A Clinician Administered Dissociative States Scale (CADSS) will be administered following the infusion by the physician or the staff. Ketamine and norketamine (an active metabolite) levels will be obtained at 30 minutes into the infusion and at 60 minutes (20 minutes after the infusion is terminated), the results of which will remain unavailable to all staff for each participant until all assessments are complete. The infusion will be preceded by a urine toxicology to ensure the absence of illicit substance use to minimize the risk of adverse interactions. Female participants will also be tested for pregnancy. Following the infusion, participants will undergo close monitoring, and prior to discharge (occurring at least 3 hrs post-infusion) psychiatric/medical clearance and a field sobriety test.

[figure not shown]

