The sitter, an ACLS certified physician, will also monitor for any side effects. Nausea and vomiting will be treated supportively and, if severe, with anti-emetic agents. So as to reduce the risk of nausea, vomiting, and aspiration, participants will be NPO after midnight prior to infusions. Anxiety and agitation will also be treated supportively and with relaxation exercises. If these side effects do not remit with such measures, and/or if the participant persists in asking that the session be stopped, the administration of ketamine will be discontinued. In other studies utilizing comparable doses of ketamine infusion, anxiety, psychosis and perceptual changes have always spontaneously resolved within 30 minutes of terminating the infusion, often within 5 minutes. Intramuscular preparations of midazolam and/or thiothixene will be kept available at the central pharmacy in order to rapidly control a ketamine-induced level of emotional distress, psychosis, or delirium should it persist. Any participant requiring pharmacotherapy to control a psychiatric complication of drug administration will be removed from the study, kept overnight for observation, and given referrals, if necessary, the next day, assuming the person can be safely discharged from hospital.

The administration of subanesthetic ketamine IV also induces a modest rise in vital signs. During the ketamine infusion, vital signs (blood pressure and heart rate) will be monitored every five minutes beginning five minutes before the infusion begins, and will be monitored after the infusion until baseline vital signs are restored. If  $HR > (220 - \text{patient age}) \times 0.85$  BPM, and if systolic blood pressure increases by  $> 60$  mm or diastolic blood pressure increases by  $> 40$  mm (or  $SBP > 200$  and  $DBP > 115$ ) during the ketamine infusion, the infusion will be permanently discontinued. The blood pressure and heart rate will be monitored and if there is no decrease after 5 minutes, then nitroglycerin, clonidine, or propranolol will be administered. If high blood pressure is symptomatic, i.e., blurred vision, headache, chest pain, the subject will be transferred to the ER.

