Any medical risks from increased blood pressure will be minimized through the careful screening of potential subjects. Subjects will be excluded for baseline hypertension or any history of cardiovascular illness. In addition, an ACLS certified physician will be present during the procedure. Continuous ECG monitoring and pregnancy testing will be provided, as well.

Extensive laboratory experience suggests that sub-anesthetic ketamine generally produces transient effects without any persistent changes, but there are some data suggesting that ketamine, and glutamate modulators in general, may alter the glutaminergic system in such a way as to render vulnerable subjects more likely to

develop psychotic disorders. Previous studies, therefore, have tended to exclude participants with a personal or family history of psychosis in order to reduce the psychiatric risks that ketamine may pose. Accordingly, individuals with a personal or first-degree family history of psychosis will be excluded from this study. Furthermore, the protocol involves close monitoring and an assessment of psychiatric stability prior to discharge; this both ensures that any lingering sedation is allowed to dissipate, and that participants are closely monitored for persistent side effects. Participants will be screened by a psychiatrist and cleared for continued participation following the infusion on Week 2, Day 2, and they will also be followed twice weekly during the following phase of the trial. Subjects will be provided a number to call to reach an on-call psychiatrist (24 hours/day) should unpleasant effects occur after subjects have left the testing facility.

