Ketamine is also associated with some abuse liability, though this abuse liability is significantly lower than that of other drugs of abuse, such as cannabis, cocaine, nicotine, alcohol, benzodiazepines, or opioids. Ketamine is generally insufflated, ingested, or injected intramuscularly in the community, and is often used in combination with other substances such as gamma-hydroxy-butyrate (GHB) or 3,4-Methylenedioxymethamphetamine (ecstasy). There is a risk, therefore, that participants may seek out ketamine after becoming exposed to it, and develop problematic patterns of ketamine use during or after the study. This risk may be compounded by the fact that it is given in this study to individuals who may have an increased vulnerability to developing substance use problems in light of their dependence on cannabis. While this important risk cannot be removed entirely, various safeguards can be implemented to ensure that it is minimized, including: 1) exercising “a minor deception” and giving participants the impression that they may receive any of a number of medications during each infusion, while ensuring that the side effects and risks are clearly conveyed; this may prevent patients from identifying ketamine and subsequently seeking it out; 2) excluding participants with a history of ketamine misuse or abuse; and 3) carefully monitoring drug use to ensure that any emergent patterns of misuse or abuse of ketamine, or any other substance, is properly addressed in a timely manner. Furthermore, ketamine is administered in this study in a way that is unrepresentative of how it is commonly used in the community (slow-drip IV infusion). In addition, this slow, sustained method of administration is unlikely to lead to the acute powerful effects generally associated with heightened abuse liability.

Participants who develop a significant adverse reaction during or after the infusion (psychosis, agitation, or adverse psychological response that is persistent and/or requiring pharmacotherapy; blood pressure elevation requiring termination) will lead to the blind being broken. This will alert the participant to his or her propensity for an adverse response to the drug, thus ensuring future safety.

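### The two mandatory vital-sign rules for stopping the ketamine infusion use the same thresholds but different logic, so as written they can give opposite instructions.

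*Protocol*

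**What the plan says.** The protocol states the stopping rule twice.

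- **Study Procedures, Infusion Procedures** (printed under Phase 2). The criteria for discontinuation are "SBP elevation > 60 mm and DBP > 40, or absolute SBP>200 and DBP>115 and HR" greater than (220 − age) × 0.85. The paragraph then points to the Risks section "for more information about managing BP or HR".
- **Risks/Discomforts/Inconveniences, procedures for minimizing risks.** The sentence opens with the same heart-rate limit and continues "BPM, and if systolic blood pressure increases by" more than 60 "mm or diastolic blood pressure increases by" more than 40 mm, with SBP above 200 and DBP above 115 in brackets as an alternative. If this happens "during the ketamine infusion, the infusion will be permanently discontinued". Pressure and heart rate are then watched and, "if there is no decrease after 5 minutes, then nitroglycerin, clonidine, or propranolol will be administered".

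Later in the Risks section, "blood pressure elevation requiring termination" is listed among the reactions that lead to the blind being broken.

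**The concern.** All five numerical limits agree, so a single rule seems to have been intended. Two things differ: the connective between the systolic and diastolic rises (*and* in Infusion Procedures, *or* in Risks), and the place of heart rate (attached to the absolute limits in the first, a leading condition on all pressure criteria in the second).

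This is a safety threshold with set consequences: a permanent stop, a five-minute watch, possibly a rescue drug and, for a pressure stop, unblinding of the participant. Staff who follow the operational paragraph to the letter could continue an infusion that the Risks section says must end, or the reverse.

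**Working it through.** **Inputs.** Five conditions, with thresholds common to both paragraphs:

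- A: SBP rise > 60 mm
- B: DBP rise > 40 mm (Infusion Procedures says only DBP > 40, taken here as a rise)
- C: SBP > 200
- D: DBP > 115
- H: HR > 0.85 × (220 − age)

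The heart-rate limit is 0.85 × 199 = 169 at age 21, 0.85 × 180 = 153 at age 40 and 0.85 × 160 = 136 at age 60.

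**Literal rules.**

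- Infusion Procedures: (A and B) or (C and D and H)
- Risks: H and (A or B or (C and D))

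**Count over the 2^5 = 32 combinations.** Infusion Procedures stops in 11 and Risks in 13; 7 are common to both. So 11 − 7 = 4 stop under Infusion Procedures only (A and B true, H false) and 13 − 7 = 6 under Risks only (H true, exactly one of A and B true, C and D not both true). Total 10 of 32, in both directions.

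**Worked cases, age 40, heart-rate limit 153, assumed baseline 120/70.**

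| Reading during infusion | SBP rise | DBP rise | Infusion Procedures | Risks |
|---|---|---|---|---|
| 185/112, HR 120 | 65 | 42 | stop | continue |
| 185/85, HR 160 | 65 | 15 | continue | stop |

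**Other readings of heart rate, keeping the written *and*/*or* between the rises.**

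| HR in Infusion Procedures | HR in Risks | Disagree, of 32 |
|---|---|---|
| with absolute limits (literal) | leading condition (literal) | 10 |
| with absolute limits (literal) | separate trigger | 18 |
| condition on everything | leading condition (literal) | 6 |
| condition on everything | separate trigger | 22 |
| separate trigger | leading condition (literal) | 10 |
| separate trigger | separate trigger | 6 |

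In the last row all 6 are isolated rises (one of A and B, not both) with H false. They stop under Risks only; an example is 185/85 with HR 120.

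**Readings that also turn the *and* between the rises into *or*.** If heart rate is then a separate trigger in both places, each rule becomes A or B or (C and D) or H, and 0 of 32 disagree. If heart rate is instead taken in Infusion Procedures as a condition on every limb, that paragraph becomes the literal Risks rule, again with 0 disagreements. Both need the rise *and* to mean *or* and heart rate to be moved off the absolute limits. They yield different rules.

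**DBP > 40 as an absolute value.** If B is always met in Infusion Procedures, the literal count is 11: 8 stop under that paragraph only (A true, H false) and 3 under Risks only. The conflict does not depend on reading DBP as a rise.

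**The case against.** The strongest reply is that this is loose drafting that can be reconciled. If *and* is a list connective throughout the Infusion Procedures sentence, and the Risks wording is treated the same way, the two agree completely. That stands, and a reader who inferred a conflict under every possible reading would go too far. But the agreement is reached only by overriding the written connectives, and the two reconciling readings give different rules, so staff still cannot tell which one applies.

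A second reply is that Infusion Procedures sends the reader to Risks, which gives the full sequence of stop, watch, drug and ER transfer, and so is the detailed version of a summary. That is reasonable, but the pointer concerns management and does not say that the Risks rule replaces the one just stated. If Risks does govern, the *and* between the rises in Infusion Procedures is wrong as written.

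Third, the counts are not clinical. Exclusion criterion 9 removes hypertension above 140/90. If pre-infusion SBP is also at most 140 (an assumption), SBP above 200 implies a rise above 60, 8 combinations cannot occur, and the literal count is 9 of 24. The counts show only that the rules differ in both directions.

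Fourth, the safeguards are substantial: an ACLS-certified psychiatrist attends and may stop for an adverse event, vital signs are taken every five minutes, symptomatic high pressure goes to the ER, and "Continuous ECG monitoring and pregnancy testing will be provided, as well". About 15 completers are planned and only a modest rise is expected. This limits the harm but does not settle which rule applies.

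**Conclusion.** The point holds for the text as written. Two current, mandatory rules with identical thresholds disagree in 10 of 32 logical combinations when read literally, in both directions (4 and 6), so at least one paragraph is wrong as written. The 10 of 32 takes DBP > 40 as a rise; the absolute reading gives 11.

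Some stronger inferences are not supported:

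- Infusion Procedures should not be taken as the more protective text for an isolated rise. It is the less readily triggered: with heart rate above its limit only Risks stops the infusion, and with heart rate below it neither literal rule does.
- The documents give no incidence of such readings, so no number of affected participants follows.
- Tolerability is named as the primary outcome in the Background section, but nothing ties it to this rule, so no effect on that outcome is claimed.

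This should be fixed because it is a safety threshold and the correction is cheap; the expected harm is limited.

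**What to change.** State one rule once in Infusion Procedures and have the Risks section refer to it. Suggested default, for the investigator to confirm: stop permanently if any one of these occurs:

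- SBP rise > 60 mm
- DBP rise > 40 mm (with the word rise written out)
- SBP > 200 together with DBP > 115, as both paragraphs now have it
- HR > 0.85 × (220 − age)

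This drops no stop that either literal rule requires. It also allows a stop on pressure alone, which the unblinding sentence presupposes and the literal Risks rule does not permit.

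It is a protective clinical choice and goes beyond harmonising. It stops in 29 of 32 combinations, while the two literal rules together stop in 11 + 13 − 7 = 17, so 29 − 17 = 12 combinations are new. Examples are heart rate alone above its limit and an isolated SBP rise of 65 with heart rate below it. The downside is possibly a few more stopped infusions; the documents give no frequency. If the investigator wants heart rate to be a condition on the pressure criteria, that can be written instead, provided it is the only version.

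Cost: a wording amendment to two paragraphs with the usual review. No new measurements are needed, since pressure and heart rate are already monitored every five minutes.

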## Lay Summary of Proposed Research

Lay Summary of Proposed Research

This project will evaluate the effect of one or two sub-anesthetic infusions of ketamine (0.11 mg/kg 2-min bolus followed by 0.6 mg/kg over 50 minutes or 1.3 mg/kg over 90 minutes) in 15 treatment-seeking cannabis-dependent individuals receiving motivational enhancement therapy (MET) and mindfulness-based relapse prevention (MBRP) therapy, using a 6-week single-blind, open label trial.

During the first two weeks of study, the participants will receive MET. In Week 2, Day 2, the participants will be asked to initiate abstinence, and receive a single infusion of ketamine on the day of abstinence initiation. In weeks 3-6, the participants will receive MBRP. If the participants are not doing well, they will receive a second infusion of ketamine in Week 4, Day 2.

In addition to measures of mindfulness and impulsivity, stress sensitivity tests are incorporated into the design in order to elucidate mechanisms of action.

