## Background, Significance and Rationale

### Background, Significance and Rationale

This proposal will focus on treating cannabis use disorders with a one or two sub-anesthetic infusions of ketamine (0.11 mg/kg 2-min bolus followed by 0.6 mg/kg over 50 minutes or 1.3 mg/kg over 90 minutes), a high-affinity non-competitive N-methyl-D-aspartate receptor (NMDAR) antagonist. Our preliminary research suggests that ketamine improves dependence-related vulnerabilities common to a variety of substances. We have shown that a single infusion improves motivation to quit, reduces cue-induced craving, improves non-reactivity, and reduces cocaine self-administration among non-treatment cocaine dependent individuals. We have also shown that ketamine infusions can be integrated into outpatient behavioral treatment, such as motivational enhancement therapy (MET) and mindfulness-based relapse prevention (MBRP), to address cocaine use disorder and alcohol use disorder. This includes a protocol with cocaine users that provides up to 2 ketamine infusions. In these protocols, some individuals who had been using cannabis problematically in addition to the substance for which they sought treatment stopped using cannabis.

In this single blind, open label trial, we extend the treatment model we have developed to treat cocaine use disorder to the treatment of cannabis use disorder, with the expectation that we will observe similar feasibility. This protocol includes a manualized sequence of MET and MBRP in conjunction with up to 2 infusions of ketamine. The primary outcome is tolerability of study medications.

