## Blood and other Biological Samples

Please create or insert a table describing the proposed collection of blood or other biological specimens. Two vials of blood will be drawn during the screening process amounting to 10 cc ( $\frac{3}{4}$  tbsp). This is to determine if there are abnormalities that preclude enrollment into the study. The tests to be run are CBC, chem.-20 with LFTs, and b-HCG (for females). During the study, ketamine and norketamine levels will be obtained  $\frac{1}{2}$  hour into the infusion and 20 minutes after it is terminated; samples are frozen at -20 C and packaged in dry ice before being sent to the Nathan Kline lab. These samples will require about 10 cc (1 tbsp).

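### The second ketamine/norketamine sample is given two times that agree only for a 40-minute infusion, and neither planned infusion lasts 40 minutes

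*Protocol*

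**What the plan says.** Under Study Procedures, the Infusion Procedures paragraph sets two blood draws for drug levels: "levels will be obtained at 30 minutes into the infusion and at 60 minutes (20 minutes after the infusion is terminated"). It states one sampling rule and does not distinguish the first infusion from the second.

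The same paragraph gives the first infusion as "0.11 mg/kg 2-min bolus followed by 0.6 mg/kg over 50 minutes" and the second as "1.3 mg/kg over 90 minutes". The Lay Summary and the Background section give the same durations: "0.11 mg/kg 2-min bolus followed by 0.6 mg/kg over 50 minutes or 1.3 mg/kg over 90 minutes".

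The section Blood and other Biological Samples repeats the sampling times without any 60-minute figure: the samples are taken half an "hour into the infusion and 20 minutes after it is terminated".

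The Procedures (by week) table marks the drug-level row in the same two columns as the infusion row (2B and 3B), so the sampling instruction applies at both infusions.

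**The concern.** One draw has two times attached to it, and they conflict for both planned infusions. Staff who work by the clock and staff who work from the end of the infusion would take different samples under the same label.

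At the first infusion both readings give a post-infusion sample, at different delays. At the second infusion they differ in kind: the clock time gives a level while the drug is still running, and the parenthesis gives a level after it has stopped. If practice varied between participants, levels from the same infusion would not share a sampling time. If the clock were followed throughout, the draw would fall on opposite sides of the infusion's end at the two infusions.

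The results are withheld from staff until a participant's assessments are complete, so the values themselves would not reveal a mistimed draw in time to correct it.

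**Working it through.** **Inputs**

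- Clock time of the second sample: 60 min (Infusion Procedures).
- Delay after the end of the infusion: 20 min (Infusion Procedures; also Blood and other Biological Samples).
- First infusion: 2-min bolus + 50 min (Infusion Procedures, Lay Summary, Background).
- Second infusion: 90 min (same places). The text leaves open whether a 2-min bolus also precedes it, so both cases are shown.

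**Can the plan's own equation be reproduced?**

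The sentence equates 60 min with end + 20 min. The implied duration is 60 − 20 = 40 min. The protocol plans no 40-minute infusion.

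**Planned durations put in**

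For an infusion ending at minute D on the chosen clock:

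- time of the post-termination draw = D + 20
- gap between the two instructions = (D + 20) − 60
- position of a 60-minute draw relative to the end = 60 − D

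| Infusion and clock | D | D + 20 | Gap | 60 − D |
|---|---|---|---|---|
| First, from start of slow infusion | 50 | 70 | 10 | +10 (after end) |
| First, from start of bolus | 52 | 72 | 12 | +8 (after end) |
| Second, no bolus or from start of slow infusion | 90 | 110 | 50 | −30 (before end) |
| Second with bolus, from start of bolus | 92 | 112 | 52 | −32 (before end) |

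**Shift between infusions if the clock time is followed at both**

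8 − (−30) = 38 min; 8 − (−32) = 40 min; 10 − (−30) = 40 min. The same nominal draw moves by 38–40 minutes relative to the end of the infusion.

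**An alternative reading**

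Suppose the 60 minutes were counted from the first sample. The draw would then be at 30 + 60 = minute 90. That is 90 − 52 = 38 to 90 − 50 = 40 min after the end of the first infusion. For the second it is 90 − 90 = 0 to 90 − 92 = −2 min relative to the end. Neither is 20 minutes after the end, so this reading does not rescue the sentence.

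The 30-minute sample falls within every planned infusion and is not affected.

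**The case against.** The strongest case against concerns weight. The protocol states: "The primary outcome is tolerability of study medications". It gives the levels no role in an aim, a stopping rule or a safety action, and it describes no analysis of them. The second infusion, where the gap is large, is given to participants only "if they have been unable to attain abstinence", and how many that will be is unknown. At the first infusion, planned for everyone, both readings give a post-infusion sample and differ by 10–12 minutes. All of this stands, and it limits the seriousness of the point.

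The section on biological samples also gives one workable time that suits both durations and agrees with the parenthesis, so a reader can guess the intent. That is fair, but the Infusion Procedures still carry the 60-minute figure and nothing says which section takes precedence. The agreement makes 60 minutes the likely mistake without proving it, since the two passages may share a common source.

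Finally, levels at the two infusions would differ even with perfect timing, because the planned amounts and durations differ. That is also correct. A common time anchor makes the sampling times comparable; it does not make the levels equal. It remains true that an on-infusion level and a post-infusion level should not be recorded as the same measurement.

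**Conclusion.** The contradiction is real. It rests only on the protocol's own durations and holds however the bolus is counted. The two instructions are 10–12 minutes apart at the first infusion and 50–52 minutes apart at the second, where the stated clock time falls 30–32 minutes before the infusion ends. Following that clock time would also breach the section on biological samples.

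The consequence is limited to the drug-level data; sample size and the primary outcome are not affected. The calculation assumes infusions run for their planned durations. Only an infusion stopped at minute 40 would satisfy both instructions. The point should be corrected, but it does not threaten the trial's main conclusion.

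**What to change.** In Infusion Procedures, delete the 60-minute clock time and set the second sample at 20 minutes after the actual end of the infusion, for both infusions. This matches the existing parenthesis and the section on biological samples, and it still works if an infusion is stopped early. Record the actual stop time and the actual draw time.

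If the sponsor did intend a fixed clock time, state it separately for each infusion, say whether the clock starts at the bolus or at the slow infusion, and delete the post-termination wording from both sections.

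The cost is a line or two of wording. The number of blood draws does not change.
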